2.2. Timings of Analyses

The final analysis may be carried out once all subjects have completed the final study visit or terminate early from the study. No personnel directly involved with the conduct of the study shall have access to the unblinded data before the completion of the trial in order to avoid introducing bias to the remaining study data.

An interim analysis may be conducted for the submission of the regulatory registration of nemolizumab.

An independent data monitoring committee (IDMC) will review and monitor subject safety throughout the study, and an independent adjudication committee (IAC) will review all asthma-related adverse events throughout the study. Details on the IDMC and IAC, including the plan of analysis for outputs; the composition of the committees; and the procedures, roles, responsibilities, and communications are provided in the respective IDMC (v1.0, dated 24-Aug-2020) and Appendix 2 of IAC charters (v1.0, dated 27-Aug-2020).

This document is confidential.

3. Study Objectives

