13.1. Adverse Events

AEs will be coded using Medical Dictionary for Regulatory Activities (MedDRA) Version 24.1.

Treatment-emergent AEs (TEAEs), defined as those AEs occurring after the first administration of study treatment until the end of the follow-up period, will be tabulated in frequency tables by System Organ Class (SOC) and Preferred Term (PT) based on the MedDRA for treatment and follow-up periods. Missing date information will be handled using the algorithm described in [Section 8.3](#).

TEAEs during treatment period are defined as AEs with onset date on or after the first dose date till 4 weeks after the last treatment or early discontinuation date whichever is earlier. TEAEs during follow-up period are defined as AEs with onset date post treatment period (4 weeks after the last treatment or early discontinuation date, whichever is earlier) to follow-up visit date.

AEs will be summarized using the number and percent of subjects reporting each SOC and PT and sorted alphabetically by SOC and by descending frequency of PT within SOC.

Subjects who experienced multiple events within the same SOC will be counted once in the SOC summary. Subjects who experienced multiple occurrences of events with the same PT will be counted once in the PT summary.

When summarizing by causality or maximum severity, if a subject experiences more than 1 occurrence of the same AE, the occurrence with the greatest severity and the closest association with the study drug will be used in summary tables. TEAEs related to study drug/study procedure are those that are identified as reasonable possibility. If relationship or severity are missing, the event will be considered as AE related to study drug/study procedure or severe AE.

An AESI is a noteworthy treatment-emergent event for the study drug that should be monitored closely and reported promptly. An AESI can be either serious or non-serious. Based on the potential risks of Nemolizumab and the risks associated with biologics in general (i.e., class effects), the following AEs will be considered as AESIs:

- Injection-related reactions,
- Newly diagnosed asthma or worsening of asthma,

This document is confidential.

- Infections
- COVID-19 infections
- Peripheral edema: limbs, bilateral,
- Facial edema
- Elevated ALT or AST ($> 3 \times \text{ULN}$) in combination with elevated bilirubin ($> 2 \times \text{ULN}$).

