Exposure-adjusted incidence rates of TEAEs is defined as the number of subjects exposed to treatment and experiencing a certain event divided by the total time of all subjects who are at risk for the event. Specially, for subjects with no event the exposure time is the time from the first drug intake to the end of treatment period. Exposure years is calculated as last study drug exposure date minus first study drug exposure date plus one, divided by 365.25 which is the number of days count in a year. This exposure year calculated for each subject is then added cumulatively and is derived for each treatment arm. So each treatment arm will have one value for exposure years (also known as "patient years"). The exposure year calculation is different in case of subjects who have completed the study or discontinued from the study or having withdrawn from the study due to any reason. Only the event occurred during the treatment period will account for calculation.

Subject listings will be presented for all

This document is confidential.

- TEAEs,
- TEAEs of special interest,
- Serious TEAEs,
- Severe TEAEs,
- TEAE leading to permanent discontinuation of study drug,
- TEAEs leading to deaths.
- Pre-treatment AE

13.2. **Laboratory Evaluations**

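### SAP 13.1 gives person-time rules for the exposure-adjusted adverse event rate that cannot all hold, plus an exception with no content

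*SAP*

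**What the plan says.** SAP 13.1 plans rates per 100 patient-years for treatment-period events, all-causality and drug-related. The Index of Tables lists them by system organ class and preferred term as Tables 14.3.1.4 and 14.3.1.5. One paragraph supplies the person-time:

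- The number of subjects with the event is "divided by the total time of all subjects who are at risk for the event". Someone without the event is counted from first dose until the treatment period ends.
- A second formula then appears: "Exposure years is calculated as last study drug exposure date minus first study drug exposure date plus one, divided by 365.25". These values are added up within each arm, with the result that "So each treatment arm will have one value for exposure years".
- An exception comes next: "The exposure year calculation is different in case of subjects who have completed the study or discontinued from the study or having withdrawn". No alternative calculation is given for any of these groups.
- For the numerator, "Only the event occurred during the treatment period will account for calculation". Earlier in 13.1, treatment-period events are those with "onset date on or after the first dose date till 4 weeks after the last treatment or early discontinuation date whichever is earlier".

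Elsewhere, SAP 8.2 ends the treatment period at Week 24. For early discontinuation it ends 28 days after the last dose, or at early termination if that is sooner. SAP 8.2 also equates last treatment with the last injection, and SAP 9.6 computes treatment duration from injection dates in the same last-minus-first-plus-one form.

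**The concern.** The first definition varies by event: the time at risk for one preferred term is not the time at risk for another. The second gives one number per arm for all terms. Both cannot be the denominator of the same rate.

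The third statement removes the base formula from almost everyone. SAP 2.2 says "The final analysis may be carried out once all subjects have completed the final study visit or terminate early from the study", so at that point every subject has completed, discontinued or withdrawn, and each falls under an exception that is not described.

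The term for the last exposure date is also undefined. If it means the last injection, the denominator stops about four weeks before the numerator does.

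Safety against placebo is the secondary objective, and relapsers leave the study, so follow-up may differ by arm. These are the planned adverse event tables that adjust for that difference. If the rule is settled only at programming, the choice could be made after unblinding.

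**Working it through.** The plan states no rate or person-time figure, so there is nothing to reproduce. The check is direct person-time arithmetic.

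**Inputs.** Week 20 is Day 141 and Week 24 is Day 169 (SAP 8.4, Table 8-1). The last dose is at Week 20 (SAP 4.1). Events count to 28 days after the last dose (SAP 13.1). Visit windows are ±5 days at Weeks 20 and 24 (SAP Table 4-1).

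**One subject, last exposure read as last injection**

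- On-schedule completer: formula 141 − 1 + 1 = 141 days; event window to 141 + 28 = Day 169; 169/141 = 1.20.
- One dose only: formula 1 day; event window up to 1 + 28 = 29 days.
- Three doses: formula 57 days; event window up to 85 days; 85/57 = 1.49.

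**One arm.** Assume 20 on-schedule completers, of whom k have the event on the stated day.

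- Last-injection formula: 20 × 141/365.25 = 7.72 patient-years (PY).
- One arm total to the end of the period: 20 × 169/365.25 = 9.25 PY.
- Event-specific time, k = 1, Day 29: (19 × 169 + 29)/365.25 = 8.87 PY.
- Event-specific time, k = 5, Day 29: (15 × 169 + 5 × 29)/365.25 = 7.34 PY.
- Event-specific time, k = 5, Day 85: (15 × 169 + 5 × 85)/365.25 = 8.10 PY.

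Rates per 100 PY:

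| Case | Last-injection formula | One total to end of period | Event-specific |
|---|---|---|---|
| k = 1, Day 29 | 13.0 | 10.8 | 11.3 |
| k = 5, Day 29 | 64.8 | 54.0 | 68.1 |
| k = 5, Day 85 | 64.8 | 54.0 | 61.7 |

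Against event-specific time with k = 5, the last-injection formula is 5% too low for Day 29 onset (64.8/68.1 = 0.95) and 5% too high for Day 85 onset (64.8/61.7 = 1.05). The direction therefore depends on incidence and timing. For scale, 1 event on 9.25 PY has an exact Poisson 95% interval of 0.3 to 60 per 100 PY.

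**Two arms with unequal exits.** Assume 18 of 20 nemolizumab and 8 of 20 placebo subjects complete, and the rest stop after one or three doses with termination 28 days after the last. Divide full-period days by last-injection days:

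- One dose: nemolizumab (18 × 169 + 2 × 29)/(18 × 141 + 2 × 1) = 3100/2540 = 1.22; placebo (8 × 169 + 12 × 29)/(8 × 141 + 12 × 1) = 1700/1140 = 1.49.
- Three doses: nemolizumab (18 × 169 + 2 × 85)/(18 × 141 + 2 × 57) = 3212/2652 = 1.21; placebo (8 × 169 + 12 × 85)/(8 × 141 + 12 × 57) = 2372/1812 = 1.31.

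On these assumptions the choice of rule changes the between-arm rate ratio by about 8% (1.309/1.211) to 22% (1.491/1.220).

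**End date.** Protocol 9.4 keeps a subject with a missed dose in the visit schedule. If only the Week 20 dose is missed, the last injection is Day 113. The formula then gives 113 days, the 13.1 window ends on Day 113 + 28 = 141, and the 8.2 period for a completer ends on Day 169. Visit shifts alone can also separate the last two. An injection on Day 136 ends the 13.1 window on Day 164, against a Week 24 visit as late as Day 174. An injection on Day 146 gives Day 174, against a visit as early as Day 164. The gap is up to 10 days either way.

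**The case against.** The strongest reply is that this is loose drafting around a workable rule. SAP 8.2 already ends the treatment period differently for completers and early discontinuers, and that could be what the exception refers to. The SAP never actually says that the clock stops at first onset; this is inferred from the reference to subjects at risk and the separate rule for those with no event. The 141-day figure needs the last exposure date to mean the last injection, yet 13.1 uses a different term from 8.2 and 9.6. The missed-dose example assumes that the subject counts as a completer, and the 10-day figure assumes that Week 24 means the actual visit; at nominal Day 169 the gap is at most 5 days. The tables are descriptive, tentatively planned and imprecise.

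Much of this stands as a limit on size. The stopping rule is inferred, the 1.20 factor disappears if exposure runs to the end of the treatment period, and the end-date gaps depend on how subjects and visits are classified. None of it removes the conflict. The exception does not cite 8.2, and a single total per arm still cannot be time at risk for each term. Nothing in SAP 8.2, 9.6, 14 or the example code chooses between the rules. The SAP's own use of injection dates favours the 141-day reading.

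**Conclusion.** The concern holds. SAP 13.1 gives rules that cannot all be applied, and its exception has no content. On the reading that the SAP's own usage favours, the formula omits up to 28 days in which events are counted. That is a factor of 1.20 in full-window time for an on-schedule completer and far more for a subject who leaves after one dose.

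The effect is confined to Tables 14.3.1.4 and 14.3.1.5. No test or confidence interval is planned for them, and the crude incidence tables do not change. The illustrative shifts rest on assumed arm sizes, onset days and retention, and in the single-arm example they are small against sampling error. The real effect on the comparison between arms cannot be determined from the documents; the unequal-exit example shows only that it need not cancel. This should be corrected before unblinding, but it does not touch the primary analysis.

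**What to change.** State one rule in SAP 13.1. For each system organ class and preferred term, a subject's time at risk runs from first dose to the earlier of first onset of that event and the end of the event window used for the numerator. Sum by arm for each term.

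Use one end date for numerator and denominator. For example, apply the existing 13.1 cut-off (last injection plus 28 days, or early discontinuation date if earlier) to every subject, completers included, and say in SAP 8.2 that it governs the adverse event period tables. Define that early discontinuation date once, because 8.2 speaks of early termination instead and a subject may stop drug yet stay in the study. A missed Week 20 dose or a shifted visit then cannot create a mismatch.

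Delete from 13.1 the last-minus-first formula, the sentence giving one value per arm and the undefined exception. Leave treatment duration in 9.6 as it is. A single total per arm over the same window would also be workable if stated, but event-specific time keeps the SAP's opening definition.

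The cost is wording in 13.1, a clarifying sentence in 8.2 and one derived time-at-risk variable per term. No new data are needed.

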13.2.1. Clinical Laboratory Evaluations

The hematology laboratory analyses, clinical chemistry laboratory analyses, and urinalyses will be performed at a central laboratory. Reference ranges will be supplied by the central laboratory and used by the investigator to assess the laboratory data for clinical significance and pathological changes. Reference ranges will be provided in the laboratory manual.

The following parameters will be reported for laboratory data.

- **Hematology:** Hemoglobin, hematocrit, white blood cell (WBC) count (with differential including eosinophils), red blood cell (RBC) count, platelet count, and mean cell volume (MCV).
- **Chemistry:** Creatinine, aspartate aminotransferase (AST), alanine aminotransferase (ALT), gamma glutamyl transferase, alkaline phosphatase, lactate dehydrogenase, total bilirubin, direct bilirubin, albumin, total protein, uric acid, sodium, potassium, calcium, chloride, glucose, urea, total cholesterol, triglycerides, low-density lipoprotein, high-density lipoprotein, creatine phosphokinase (CPK). CPK isoenzyme test will be performed only if CPK is elevated to $>2.5 \times$ upper limit of normal (ULN).
- **Urinalysis:** pH, glucose, ketones, blood, protein, leukocytes, nitrites, bilirubin, urobilinogen, and specific gravity.

Laboratory assessments are performed at Baseline/Day 1, Week 12, Week 24, Early Termination and Week 32/Follow-up.

Hematology and chemistry laboratory data (absolute values and change from Baseline) will be summarized as continuous variables by visit (Baseline and scheduled visits only). Urinalysis laboratory data will be summarized by visit (Baseline and scheduled visits only). Last post-baseline, worst post-baseline and maximum post-baseline results will also be included in the summaries and will include unscheduled visits

This document is confidential.

in the derivation. Worst post-baseline value will be defined as the highest or lowest value relative to the reference range. Parameters will be presented in alphabetically order.

Shift tables will be generated using the reference ranges (Low, Normal, High and Missing) for hematology and chemistry laboratory data. The number and percentage of subjects shifting from reference ranges between Baseline and each visit (scheduled visits only) will be summarized. Last, worst and maximum post baseline values will also be included in the shift tables and will include unscheduled visits in the derivation.

Summary of the number and percentage of subjects who met criteria of potential clinically significant (CS) value will be summarized (scheduled visits only) for hematology, chemistry. Last, worst and maximum post-baseline results will also be included in the summaries. Potentially CS ranges are listed in [Section 20.2](#).

For statistical and graphical summaries of the laboratory tests, values below or above the limit of detection (e.g. '< 3' or '> 500') are substituted with the lower limit of detection minus 1% for values below the lower limit and are substituted with the upper limit of detection plus 1% for values above the upper limit (e.g. '< 3' is substituted by '2.97', '> 500' is substituted by '505'). In data listings, the values are shown including the < or > sign.

Distribution of continuous hematology and chemistry laboratory data (in particular, Aspartate Aminotransferase (AST), Alanine Aminotransferase (ALT), Alkaline Phosphatase (ALP), Total Bilirubin (BILI), Creatinine Kinase (CK) and Leukocytes (WBC)) will be displayed graphically as boxplot by treatment group for baseline and for each scheduled visits and the maximum post-Baseline (including unscheduled visits in the derivation) values.

By-subject listing will be presented for all laboratory data. By-subject listing for subjects with at least one abnormal result (out of reference range) will be provided for hematology and clinical chemistry. By-subject listing for subjects with at least one potentially CS result will be provided for hematology, clinical chemistry.

All laboratory data will be listed for the Safety population.

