**Table 3. Treatment Summary**

LTE Lead-in Study	Lead-in Study Assigned Treatment	Dose Q4W for 24 weeks a
RD.06.SPR.202699	Nemolizumab 30 mg (1 injection)	Blinded Nemolizumab 30 mg (1 injection)
	Nemolizumab 2 × 30 mg (2 injections)	Blinded Placebo (1 injection)
		Blinded Nemolizumab 2 × 30 mg (2 injections)
		Blinded 2 × Placebo (2 injections)

Abbreviation: LTE = long-term extension; Q4W = every 4 weeks.

aDose will be assigned based on dose received in LTE lead-in study.

Clinical assessments will occur according to the Schedule of Assessments in the protocol through the Week 24 visit.

If a subject meets the criteria for relapse at any point, the subject will exit the study and re-enter the LTE study (see [Figure 2](#)). Subjects who exit the study before Week 24 should complete an early termination (ET) visit. Subjects who complete the study through Week 24 are eligible to re-enroll in the LTE study.

Subjects who prematurely discontinue study drug for reasons other than relapse will be encouraged to complete the scheduled study visits. These subjects will only be eligible for re-enrollment in the LTE study if they continue with study visits through Week 24.

Subjects who discontinue the study for reasons other than relapse before Week 24 or who will not continue nemolizumab treatment in the LTE study should complete a follow-up visit, 12 weeks ( $\pm 7$  days) after the last study drug injection.

[figure not shown]

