Subjects who prematurely discontinue study drug for reasons other than relapse will be encouraged to complete the scheduled study visits. These subjects will only be eligible for continued treatment with nemolizumab in the LTE study if they continue with study visits through Week 24.

When a subject is withdrawn from the study, he/she will be fully assessed whenever possible, and followed according to guidelines presented in Section 10.3.1 (ET Visit).

Reasonable efforts will be made to contact subjects who are lost to follow-up. These efforts must be documented in the subject's file.

The Sponsor has the right to terminate the study at any time in case of SAEs or if special circumstances concerning the investigational product or the company itself occur, making further treatment of subjects impossible. In this event, the Investigator(s) will be informed of the reason for study termination.

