**Table 7. Schedule of Assessments**

	Baseline a	Treatment Period							FU	ET	Unscheduled
		V1	V2	V3	V4	V5	V6	V7			
Visit	V1	W4	W8	W12	W16	W20	W24	W32	if applicable b	if applicable c	
Week	W0 (Day 1)	W4	W8	W12	W16	W20	W24	W32			
Visit Window (days)		±1	±3	±3	±3	±5	±5	±7			
ICF a	X										
Inclusion/exclusion criteria	X										
Demographics	X										
Medical history, previous therapies and procedures, smoking status	X										
Patient-Reported Outcomes											
PP NRS/ SD NRS d, e	X-----					X			X		(X)
DLQI e	X				X		X		X		(X)
Efficacy Assessments											
IGA	X	X	X	X	X	X	X		X		(X)
Safety Assessments											
ACT e, f	X	X	X	X	X	X	X	X	X		(X)
Respiratory examination	X	X g	X g	X	X g	X g	X	X	X		(X)
PEF testing	X	X g	X g	X	X g	X g	X	X	X		(X)
Vital signs h	X	X	X	X	X	X	X	X	X		(X)
Full physical examination	X			X			X	X	X		(X)
Symptom-directed physical examination		X	X		X	X					
Height	X										(X)
Weight	X						X		X		(X)
12-lead ECG i	X						X		X		(X)
Contraceptive counseling	X										(X)

This document is confidential.

	Baseline a	Treatment Period							FU	ET	Unscheduled
		V1	V2	V3	V4	V5	V6	V7			
Visit	W1	W4	W8	W12	W16	W20	W24	W32	if applicable b	if applicable c	
Week	W0 (Day 1)	W4	W8	W12	W16	W20	W24	W32			
Visit Window (days)		±1	±3	±3	±3	±5	±5	±7			
Adverse events e	X	X	X	X	X	X	X	X	X		(X)
Concomitant therapies and procedures e	X	X	X	X	X	X	X	X	X		(X)
Laboratory Assessments											
Blood samples for hematology and clinical chemistry j	X			X			X	X			(X)
Urinalysis	X			X			X	X			(X)
Urine pregnancy test k	X	X	X	X	X	X	X	X	X		(X)
FSH l	X										(X)
Blood sample for virology (HIV, Hepatitis B and C test)											(X)
Blood sample for TB test											(X)
POE & Immunogenicity Assessments											
Blood sample for POE c, m	X						X		X		(X)
Blood sample for ADA c, m	X						X		X		(X)
Study Drug Administration											
Randomization	X										
Study drug injection n, o, p, q, r	X	X	X	X	X	X					(X)

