ACT = Asthma Control Test; ADA = anti-drug antibody; AE = adverse event; DLQI = Dermatology Life Quality Index; ECG = electrocardiogram; ET = early termination; FSH = follicle-stimulating hormone; FU = follow-up; HIV = human immunodeficiency virus; ICF = informed consent form; IGA = Investigator Global Assessment; LTE = long-term extension; PEF = peak expiratory flow; POE = proof of exposure; PP NRS= peak pruritus numeric rating scale; SD NRS= sleep disturbance numeric rating scale; TB = tuberculosis; UPT = urine pregnancy test; V = visit; W = week.

- a) After signing the ICF, all subjects will be evaluated for study participation, based on eligibility criteria. The Week 52 study assessments from the LTE lead-in study RD.06.SPR.202699 will be used as baseline assessments for the current study.
- b) Subjects who relapse or discontinue prematurely (before the Week 24 visit) should complete an ET visit. If the subject discontinues for reasons other than relapse before Week 24, or will not continue with nemolizumab treatment in the LTE study, a follow-up visit should also be completed, 12 weeks ( $\pm 7$  days) after the last study drug injection.
- c) Assessments to be conducted at the unscheduled visit depend on the reason for the visit. POE and ADA analyses should only be performed at unscheduled visits that are conducted for safety reasons when safety labs are collected for the management/monitoring of an AE. When a series of unscheduled visits is needed for the monitoring of the same AE, the POE and ADA collection is not required if already done at the first unscheduled visit of the series. Additional collection of samples for POE and ADA analysis should be performed per Investigator's judgment.
- d) PP NRS to be recorded by subjects once daily in the evening. SD NRS to be recorded by subjects once daily in the morning and if possible, within 1 hour of getting out of bed.
- e) Patient-reported outcome assessments and designated safety measurements (including AE and concomitant therapies/procedures assessments) should occur before Investigator assessments, laboratory sample collections, and study drug administration.
- f) Subjects with a history of asthma will complete the ACT testing at all visits. Subjects with a new (de novo) diagnosis of asthma will complete the ACT testing beginning from de novo diagnosis and at all subsequent scheduled visits.

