13.5. Physical Examination

Following body system assessments will be performed at Baseline/Day 1, Week 12, Week 24, Early Termination, and Week 32/Follow-up:

- Head, ears, eyes, nose, throat, neck (including thyroid),
- Skin/integumentary system (excluding PN),
- Cardiovascular system,
- Respiratory system,
- Gastrointestinal system,
- Musculoskeletal system,
- Lymph nodes,
- Nervous system, and
- Extremities.

The number and percentage of subjects with physical examination results by body system classified as 'Normal', 'Abnormal, NCS' or 'Abnormal, CS' will be summarized (Baseline and scheduled visits only).

Shift from Baseline of the physical examination category will also be summarized by body system.

This document is confidential.

By-subject listing will be provided for subjects who have at least one abnormal result from any body system or who missed the assessment due to any reason.

All physical examination results will be listed on the Safety population.

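### SAP 13.2.1 places laboratory tests at early termination, but both schedules of assessments leave that cell blank, so subjects who relapse before Week 24 and re-enter the LTE have no laboratory draw required at exit

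*SAP*

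**What the plan says.** **Laboratory visits, SAP text.** SAP 13.2.1 names five: "Laboratory assessments are performed at Baseline/Day 1, Week 12, Week 24, Early Termination and Week 32/Follow-up".

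**Laboratory visits, schedules.** In Protocol Table 7 the row "Blood samples for hematology and clinical chemistry" and the urinalysis row are marked at Baseline, Week 12, Week 24 and Week 32, with a conditional mark for unscheduled visits and nothing at ET. The same rows in SAP Table 4-1 also have a blank cell before the unscheduled mark. Protocol 12.5 tells sites that samples are obtained at the visits given in Table 7.

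**Who has an ET visit.** Table 7, footnote b: "Subjects who relapse or discontinue prematurely (before the Week 24 visit) should complete an ET visit". The text after Protocol Table 3 says of relapse: "If a subject meets the criteria for relapse at any point, the subject will exit the study and re-enter the LTE study".

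**Who has the follow-up visit, where laboratory tests are marked.** Footnote b adds it for a restricted group: "If the subject discontinues for reasons other than relapse before Week 24, or will not continue with nemolizumab treatment in the LTE study". A relapser who returns to the LTE is outside that group.

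**General wording on withdrawal.** Protocol 8.3: "When a subject is withdrawn from the study, he/she will be fully assessed whenever possible". It then refers to Section 10.3.1, which lists no ET procedures.

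**The concern.** The SAP describes laboratory data that the schedule does not ask sites to collect. The gap falls on the subjects whose exit defines the primary endpoint. In a randomized withdrawal design relapse is expected more often on placebo, so exit laboratory results are likely to be missing unequally by arm.

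The secondary objective is safety against placebo. SAP 13.2.1 reports last, worst and maximum post-baseline values, and carries them into the shift and potentially-clinically-significant tables. For an early relapser these values rest on Week 12 or on nothing, apart from any unscheduled sample. One adverse event of special interest in Protocol 12.7.2 is defined by ALT or AST together with bilirubin, which come from the same samples.

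**Working it through.** The plan gives no figure to reproduce, so the check compares the texts and then sizes the gap.

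**Step 1. Is the ET column readable, and was it used for other safety items?** The row "Full physical examination" in Table 7 serves as a control, because SAP 13.5 describes that examination in the same way: "Following body system assessments will be performed at Baseline/Day 1, Week 12, Week 24, Early Termination, and Week 32/Follow-up".

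| Visit | SAP 13.2.1, laboratory | Table 7, hematology/chemistry | Table 7, urinalysis | Table 7, full physical exam | SAP 13.5, physical exam |
|---|---|---|---|---|---|
| Baseline | yes | X | X | X | yes |
| Week 12 | yes | X | X | X | yes |
| Week 24 | yes | X | X | X | yes |
| Week 32 | yes | X | X | X | yes |
| ET | yes | blank | blank | X | yes |
| Count | 5 | 4 | 4 | 5 | 5 |

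The physical-examination pair agrees at 5 and 5; the laboratory pair does not, at 5 and 4. IGA, ECG, vital signs, urine pregnancy test and the drug-concentration and antibody samples also carry an ET mark in Table 7. The gap is therefore confined to hematology, chemistry and urinalysis.

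**Step 2. What does SAP Table 4-1 add?** Its two laboratory rows hold 10 cells for 10 columns, and the ninth (ET) is blank. Other rows of that table have lost cells in the text copy: full physical examination shows 4 marks there, against 5 visits in SAP 13.5. Table 4-1 is supporting evidence only; the point rests on Table 7.

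**Step 3. Scheduled laboratory results for a relapser who re-enters the LTE.**

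- Exit before Week 12: baseline only, so no scheduled post-baseline result.
- Relapse found at the Week 12 visit: the marked Week 12 draw coincides with it.
- Exit after Week 12 but before Week 24: Week 12 only.
- Relapse found at the Week 24 visit: the Week 24 draw is available.

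**Step 4. Size.** Protocol 14.1 and SAP 4.3 plan about 40 subjects, randomized 1:1, so 40 / 2 = 20 on placebo. No relapse rate is given, so a range is assumed:

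- 20%: 20 × 0.20 = 4
- 50%: 20 × 0.50 = 10
- 80%: 20 × 0.80 = 16

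These are upper bounds on the number with no required exit draw. They still include relapses found at the Week 12 visit and relapsers who do not return to the LTE. SAP 4.1 gives about 100 subjects instead of 40; on that figure there are 50 per arm and the same rates give 10, 25 and 40.

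**Step 5. Where would ET results enter the analysis?** SAP 8.4 does not window safety data, and by-visit summaries use scheduled visits. The last, worst and maximum derivations in SAP 13.2.1 name unscheduled visits but not ET. Even if sites draw the samples, the SAP does not say where the results go.

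**The case against.** A reader might infer that every relapser leaves with no exit laboratory data. The documents do not support that.

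- ET applies only to exits before the Week 24 visit, and a relapse found at Week 12 or Week 24 coincides with a marked draw.
- Return to the LTE is not certain. Protocol 7.1 says a relapser may be considered for re-entry, and Protocol 10.3.1 calls such subjects eligible. One who does not continue nemolizumab there has the follow-up visit, with laboratory tests.
- SAP 13.2.1 says the tests are done at ET, and Protocol 8.3 asks for full assessment at withdrawal where possible. Some sites may draw the samples. The laboratory manual and Appendix 8, which give blood volumes by visit, are not visible and might show an ET draw.

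A reader might also infer that an ET draw would restore the missing Week 24 results. It would not. Fewer Week 24 results among relapsers follow from the exit rule itself, and ET results would add to the last, worst and maximum values.

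Three further arguments are weaker. Protocol 14 lets the SAP prevail over the protocol, but an analysis document cannot supply samples that sites were not scheduled to take, and the SAP's own Table 4-1 also has the blank. The full-assessment wording in Protocol 8.3 points to a section with no procedure list. Unscheduled visits in Protocol 10.3.2 are for repeat abnormal tests, adverse-event follow-up or efficacy checks tied to rescue medication, so they do not cover a routine relapse exit. They do mean that detection of the liver event does not depend on an ET draw alone.

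**Conclusion.** The contradiction is real: SAP 13.2.1 lists five laboratory visits and Table 7 marks four, with ET the one missing. If sites follow Table 7, subjects who relapse before Week 24 and re-enter the LTE have no laboratory draw required at exit. Up to about 4, 10 or 16 of 20 placebo subjects would be affected at assumed relapse rates of 20%, 50% or 80%. A higher number on placebo than on nemolizumab is the natural expectation in this design, but it is not a figure from the documents.

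The effect is on the last, worst and maximum post-baseline laboratory values and on the shift and potentially-clinically-significant tables that use them. The primary endpoint is not touched. The Table 7 cell should be confirmed against the PDF, since tables can lose cells in a text copy, but the control row makes a misread column unlikely.

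**What to change.** Reconcile four places on laboratory tests at ET: Protocol Table 7, SAP Table 4-1, Protocol 8.3 (with 10.3.1, to which it refers) and SAP 13.2.1. The SAP's stated intent is that the tests are done there. Carrying that through means marking ET in the hematology/chemistry and urinalysis rows of both tables.

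State in SAP 13.2.1 that ET results enter the last, worst and maximum post-baseline derivations, and hence the shift and potentially-clinically-significant tables.

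The cost is two cells in Table 7 by protocol amendment, the matching cells in Table 4-1, and one sentence in the SAP. For each affected subject it is one extra tube and a urine sample, at a visit that already takes place and where blood is already drawn for drug concentration and antibodies.
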